1) PROTOCOL TITLE

Comparison of botulinum toxin injections in forearm **F**lexor plus **E**Xtensor muscles versus flexor muscles alone for the treatment of **E**ssential hand **T**remor (FLEX-D ET)

2) INVESTIGATORS:

PI: [name]

CoPI: [name], MPH

3) STUDY CENTER:

Cleveland Clinic Center for Neurological Restoration, Cleveland, Ohio

4) STUDY TIMELINES (WITH A PROJECTED ENROLLMENT OF ABOUT 1/WEEK):

- First patient in → September 1, 2016
- 1/3 of patients enrolled → September 30, 2016
- 2/3 of patients enrolled → October 15, 2016
- Enrollment completed → October 30, 2016
- Last patient out → January 30, 2017
- Analysis of data → February 14, 2017

5) BACKGROUND:

ET is one of the most common movement disorders, affecting 4% of adults of 40 years of age and older (Abboud et al. 2011). Although called “benign,” ET causes substantial impairment in activity of daily living. ET typically affects both upper extremities, but it can start on one side. Progressive involvement of head, lips, tongue, legs, and voice is also a feature of ET.

Treatment is of ET is symptomatic. Propranolol and primidone are commonly used first-line agents (Simpson et al. 2008). Topiramate, gabapentin and zonisamide are also used as adjunctive or stand-alone treatment (Simpson et al. 2008). Unfortunately, 40-50% of patients do not respond to pharmacotherapy (Sadeghi and Ondo 2010). Pharmacologically refractive ET or patients who are poor candidates for pharmacotherapy often benefit from either botulinum toxin (BoNT) injection or deep brain stimulation (DBS) (Jankovic et al. 1996; Brin et al. 2001; Sadeghi and Ondo 2010). Although DBS is the standard of care for pharmacologically refractive ET, it is invasive, involves the risks of general anesthesia, and produces the side effects of dysphagia, paresthesias, and ataxia in up to 30% of patients (Larson 2014). In addition, 10-20% of patients are non-responders or experience loss of treatment efficacy (Larson 2014). Given these limitations of DBS, the relatively less invasive approach of BoNT injection is a resource that is worth a try.

Two randomized controlled trials (RCT) with somewhat similar study design assessed the efficacy of BoNT in hand ET (Jankovic et al. 1996; Brin et al. 2001) (Figure 1). Both trials used type-A BoNT (Botox®). Both trials investigated injections in wrist flexors and extensors. Injections with two strengths, 50U and 100U, were tested. The dose injected in wrist extensors was always two-third (2/3rd) of that injected in wrist flexors. But there were also some differences in trial designs. Figure 1 depicts the differences.

Figure 1

Randomized control trial 1 (Jankovic et al. 1996)	Randomized control trial 2 (Brin et al. 2001)
Comparison: BoNT versus placebo	Comparison: BoNT 50U versus 100U versus placebo
Sites: wrist flexors and extensors of dominant hand	Random assignment to a comparison group
Regimen: 50U in flexor and extensor (15 flexor carpi radialis (FCR), 15 flexor carpi ulnaris (FCU), 10 extensor carpi radialis longus and bravis (ECR), 10 extensor carpi ulnaris (ECU)) → if unsuccessful at 4 week evaluation, then double the dose at each injection site.	Site: Wrist flexor and extensor of dominant hand (FCR, FCU, ECR, ECU).
Follow-up: 2,4,6,8,12,16 weeks	Regimen: 50U = 15 FCR, 15 FCU, 10 ECR, 10ECU 100U = 30 FCR, 30 FCU, 20 ECR, 20ECU
	Follow-up: 1,2,4,6,8,12,16 weeks

Both trials reported significant improvement in tremor rating scale and objective assessment using accelerometry (Jankovic et al. 1996; Brin et al. 2001). One study reported that 75% of BoNT treated patients had mild to moderate improvement that reached statistical significance (Jankovic et al. 1996). Objective assessment of ET with limb accelerometry showed a 30% reduction in tremor intensity in 9 of 12 BoNT-treated patients and in 1 of 9 placebo-treated patients ($p < 0.05$) (Jankovic et al. 1996). Similar results were reproduced in a second RCT with much larger ($n=133$) number of ET patients (Brin et al. 2001). Results of these two RCTs led to the American Academy of Neurology level-B recommendation that BoNT should be considered for treatment of ET in patients who are refractory to oral pharmacotherapy (Simpson et al. 2008).

Both RCTs, however, presented significant caveats. Although patients had significant improvement in tremor rating scales and objective assessments, none had a change in functional rating scales. Most BoNT injected patients in both studies had finger weakness. One RCT reported worse extensor weakness (50% moderate weakness, 42% mild weakness) as compared to flexor (Jankovic et al. 1996), while the other noted “finger drop” in the BoNT injected (Brin et al. 2001). Although claimed “unrelated” in one of the trials, it is possible that lack of subjective sense of improvement evidenced by functional rating scale was related to finger extension weakness. This argument is supported by an open-label study of BoNT injection (Pacchetti et al. 2000). This open-label study electrographically identified the most involved muscles using the surface electrodes placed on the skin overlying extensor carpi radialis (ECR), extensor carpi ulnaris (ECU), flexor carpi radialis (FCR), flexor carpi ulnaris (FCU), brachioradialis, pronator teres (PT), biceps, and triceps. Only muscles that showed significant tremor were injected with BoNT, hence wrist extensors were not injected in all patients (Pacchetti et al. 2000). Although dose and distribution of injected flexor muscles varied amongst patients, only 15% of the patients had finger extension weakness (Pacchetti et al. 2000). Furthermore, there was a significant improvement in both tremor severity and functional rating scales (Pacchetti et al. 2000). It is therefore possible that poor outcome on subjective functional rating scale in both RCTs were related to weakness. In addition, both RCTs had rigid treatment protocol implementing a fixed BoNT dose in predetermined muscles regardless of the disease severity. Lack of subjective improvement in some patients enrolled in these RCTs might be due to the mismatch between administered dose and severity of symptoms; for example, higher dose for mild tremor might exaggerate weakness, while low dose for moderate to high severity tremor might lead to under treatment.

In summary, while these studies have demonstrated the potential role of BoNT for ET there remains limitations that have yet to be addressed. It is unclear if the perceived efficacy of BoNT in tremor reduction is diminished by associated extensor weakness. It is also unclear if BoNT injection of flexors alone is equally efficacious as the injection of both flexor and extensor muscles. If injecting extensor muscles is essential, can the ratio between extensor and flexor muscles be adjusted to give efficacy with no weakness? Furthermore, although previous studies have demonstrated significant objective improvement in tremor severity, they did not observe significant improvements in quality of life (QOL), functional improvement, and global improvement.

With these limitations in mind, we propose a pilot, single center, double blind, randomized, parallel, placebo controlled trial comparing 2 BoNT injection patterns for treatment of moderate to severe essential tremor. To minimize the potential for extensor weakness, we will inject the extensor muscles with 1/3 the dose used for the flexor muscles (a 3:1 ratio of BoNT injected for flexor to extensor as compared to the previous studies which used a 3:2 ratio). Our primary outcome and secondary outcomes as detailed below will include patient global impression scale as well as other functional and QOL scales.

6) STUDY OBJECTIVES:

Study aim:

To compare the efficacy of botulinum toxin (BoNT) injections in forearm flexors plus extensor muscles versus flexors alone for the treatment of essential hand tremor (ET).

Hypothesis:

We hypothesize that both patterns of BoNT injection (flexors plus extensors, flexors alone) will be equally efficacious in decreasing tremor, but that patients in the flexors alone group will experience less motor weakness and therefore report greater global improvement in symptoms.

We acknowledge the possibilities that patients in the flexors plus extensors group may perceive greater improvement in tremor severity due to the additional injection of the extensor compartment and that the injection of the extensor compartment may be well tolerated because the injected dose is only 1/3 of the dose for the flexor compartment.

Primary Outcome Measure:

Difference in 6 week post injection on a Patient Global Impression Scale-Improvement Subscale (PGI-I)

Secondary Outcome Measures:

1. *Improvement in 6 week post injection in tremor rating scale.*
2. *Difference in the mean Quality of Life in Essential Tremor Questionnaire (QUEST) at Week 6 from baseline between wrist flexors versus wrist flexors plus extensors group.*
3. *Improvement in 6 week post injection in Clinician Global Impression Scale-Improvement Subscale (CGI-I).*
4. *Difference in grip strength post injection between the two groups at 6 weeks*
5. *12 week post injection patient global improvement scale*

6. *12 week post injection tremor rating scale*
7. *Difference in the mean QUEST score at Week 12 from baseline between wrist flexors versus wrist flexors plus extensors group.*
8. *12 week post injection clinician global improvement scale*
9. *Difference in grip strength post injection between the two groups at 12 weeks.*

Tertiary Outcome Measures

1. *Monitor changes in depression using PHQ-9 at 6 weeks*
2. *Monitor changes in anxiety using GAD-7 at 6 weeks*
3. *Monitor changes in depression using PHQ-9 at 12 weeks*
4. *Monitor changes in anxiety using GAD-7 at 12 weeks*

The scales that will be used in the study are below:

Global assessment graded by patient and clinician (PGIS and CGIS respectively) on -4 to +4 scale

- -4 = severe worsening
- 0 = no change
- +4 = complete abolishment of symptoms

Tremor Rating scale (TRS) at rest, posture and kinetic

- 0 = none perceived
- 1 = slight (barely noticeable)
- 2 = moderate, noticeable, probably not disabling (<2cm excursions from affected part)
- 3 = marked, probably partially disabling (2-4cm excursions)
- 4 = severe, coarse, disabling (>4cm excursion)

Kinetic tremor will be measured using motor tasks including handwriting and pouring. Patients will be asked to write the sentence "Today is a nice day" with their dominant hand. They will also be asked to draw a spiral. Pouring will be assessed by asking the patient to pour water from one cup to another.

QUEST will also be administered at baseline and follow up visits to assess functional impairment of tremor in activities of daily living.

Grip strength will be assessed using dynamometer.

7) STUDY DESIGN/METHODS:

We propose a pilot, single center, double blind, randomized, parallel, placebo controlled trial comparing 2 BoNT injection patterns for treatment of moderate to severe essential tremor.

We will recruit 20 patients with ET. The following inclusion and exclusion criteria will be used during the screening visit.

Inclusion Criteria

1. Age 18 and over, male or female patient with ET involving at least their dominant hand, as diagnosed by a movement disorders neurologist.
2. Having bothersome hand tremor in dominant hand with a hand TRS ≥ 2
3. On stable medications during last 30 days prior to enrollment.

Exclusion Criteria

1. Presence of secondary causes of tremor, such as dystonia and parkinsonism
2. Any contraindication to botulinum toxin injections (e.g. motor neuron disease, neuromuscular junction disease, etc.)
3. History of surgical treatment for ET.
4. Dementia as defined by DSM-V criteria
5. Patients with suboptimally treated depression and significant depressive symptoms as defined by a PHQ-9 score of ≥ 15 (PHQ-9 scores 1-4 Minimal depression; 5-9 Mild depression; 10-14 Moderate depression; 15-19 Moderately severe depression; 20-27 Severe depression). Antidepressant medications, prescribed for depression or anxiety, will be allowed if the patient has been on a stable dose for at least 30 days.
6. Patients with suboptimally treated anxiety and significant anxiety symptoms as defined by a GAD-7 score of ≥ 15 (GAD-7 scores 0-4: minimal anxiety; 5-9: mild anxiety; 10-14: moderate anxiety; 15-21: severe anxiety). Anti-anxiety medications, prescribed for anxiety, will be allowed if the patient has been on a stable dose for at least 30 days.
7. Significant renal, hepatic, cardiac and thyroid disease

At the screening visit, if patient meets inclusion criteria and signs informed consent, patient will be randomized to one of two paradigms. Tremor will be rated based on Tremor Rating Scale (TRS) and Tremor Severity Scale (TSS). We will also obtain baseline evaluation of depression and anxiety, using PHQ-9 and GAD-7 respectively. In addition we will evaluate grip strength using dynamometer. Patients will be randomized to receive either injections of 150 units of abobotulinumtoxinA (Dysport[®]) in flexor compartment of dominant arm (75 units in flexor carpi radialis [FCR] and 75 units in flexor carpi ulnaris [FCU]) along with placebo in extensor carpi radialis (ECR) and extensor carpi ulnaris (ECU) or 75 units in FCR and FCU and 25 units in ECR and ECU. Injections will be done in dominant arm only. We will reduce dose in extensor by 66% of that given in flexor as opposed to previous RCTs where dose was reduced by 33% (Jankovic et al. 1996; Brin et al. 2001).

- Group 1 – plus Extensors: BoNT 200 units total (75U FCR, 75U FCU, 25U ECR, 25U ECU).
- Group 2 – Flexors alone: BoNT 150 units total (75U FCR, 75U FCU, 0UECR, 0U ECU).

The patients will be seen in follow up at 6 weeks and again at 12 weeks. At these times we will repeat all baseline measures and in addition have patients evaluate treatment response using a patient global impact scale ranging from -4 (severely worse) to +4 (no more tremor) with 0 meaning no change. Clinicians will be asked to complete the same scale. Figure 2 depicts the outline of our study design.

Figure 2: Study Design

Visit	1	2	3
Type	Screening/Baseline (injection)	Post injection week	Post injection week
Time	0	6 weeks	12 weeks
Informed Consent	X		
History and PE	X	X	X
Concomitant Meds	X	X	X
Adverse Events		X	X
TRS	X	X	X
QUEST	X	X	X
PHQ-9	X	X	X
GAD-7	X	X	X
PGIS		X	X
CGIS		X	X
Grip Strength	X	X	X

Procedure/test:

The BoNT injections will take place in a dedicated clinical research space, located in the CNR Movement Disorders clinic in the U ("Mellen") building. No other patient will be present and the door will be closed to protect patient privacy. The patients will come in the morning when tremor will be evaluated clinically. Each patient will receive BoNT injections into dominant upper extremity using protocol outlined above. We will evaluate patients at week 6 and 12 post injection. At baseline visit, the nurse who is mixing the toxin will not be blinded to the treatment arm, but both the patient and PI who will be injecting as well as administering the rating scale will remain blind.

Randomization will be done using a computer program and each subject will be assigned an envelope which nurse will have access to and open when she is mixing the agent.

Statistical analysis:

Assessment of tremor improvement - We will compare average result of PGIS and CGIS at week 6 and week 12 between two groups. Furthermore we will compute percent change of TRS and QUEST for each follow-up visit as compared to the baseline. Given the small sample size, Mann-Whitney U test will be used for calculations.

Based on the previous studies (Jankovic et al. 1996; Brin et al. 2001), mean change in TRS and PGIS was 1 point (about 25% improvement on a 4-point scale) with a standard deviation of 0.7 points at week 6 post injection. To achieve an alpha of 0.05 and a power of 80%, we estimate a sample of size of 18 total patients with 9 in each treatment group. Accounting for an estimated 10% attrition rate we will recruit 20 total patients into this trial.

We will use the above analysis to answer our primary question: Whether BoNT injections to both wrist flexors and extensors are superior as compared to injections to wrist flexors alone; or vice versa?

Confidentiality of Data:

Identifying information will be severed from study data. Subject numbers will be used to identify all participants. A password protected file linking subject numbers to identifying information will be maintained on a CNR computer. Likewise, electronic study data will be stored in password protected files and folders on a CNR computer. Any data on portable or removable device will be de-identified and protected by encryption. Paper study forms will be maintained in a locking filing cabinet in a secure area. Only the study investigators will have access to study files and folders.

Safety and Data Monitoring:

All adverse events, as reported by the subject during the study, will be documented and reported to the IRB according to the IRB policy. Any unanticipated problems will be reported to the IRB according to the IRB policy as soon as they occur or as soon as they are discovered. Efficacy data will be collected as per study protocol

Budget:

For a total of 20 patients and 3 visits per patient (Baseline, 6 weeks post injection and 12 weeks post injection) including investigator, coordinator, supplies and patient stipend we anticipate a total cost of \$48, 423. Funding will be provided by Ipsen, the manufacturer of Dysport®.

Reference List

Larson, P. S. (2014). Deep brain stimulation for movement disorders. *Neurotherapeutics : The Journal of the American Society for Experimental NeuroTherapeutics*, 11(3), 465–74. doi:10.1007/s13311-014-0274-1

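### The plan gives grip outcomes 4 and 9 no stated analysis and baseline grip no role; adjusting for baseline would gain precision if baseline and follow-up grip are at least moderately correlated

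*Combined protocol and SAP*

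**What the plan says.** **Outcome definitions (section 6, Secondary Outcome Measures).** Outcome 4 is "Difference in grip strength post injection between the two groups at 6 weeks" and outcome 9 is "Difference in grip strength post injection between the two groups at 12 weeks". Neither mentions baseline. In the same list, QUEST outcome 2 is framed "at Week 6 from baseline between wrist flexors versus wrist flexors plus extensors group", and outcome 7 is worded likewise for week 12. Tremor rating scale (TRS) outcomes 1 and 6 do not mention baseline.

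**Data collection (section 7).** At the screening/baseline visit: "In addition we will evaluate grip strength using dynamometer". For weeks 6 and 12: "At these times we will repeat all baseline measures". Figure 2 marks grip at visits 1, 2 and 3.

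**Analysis (section 7, Statistical analysis).** Baseline is used for two scales only: "Furthermore we will compute percent change of TRS and QUEST for each follow-up visit as compared to the baseline". One test is named: "Given the small sample size, Mann-Whitney U test will be used for calculations". Both sentences stand in the paragraph on tremor improvement. Grip is not named there, and no part of the document gives baseline grip a role in an analysis.

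**The concern.** Grip is the only listed outcome that measures strength, and the hypothesis in section 6 expects less weakness with flexor-only injection. The sample is small and takes adults of both sexes from age 18, so wide between-person spread in grip is a reasonable assumption. If a patient's grip at follow-up is related to grip before injection, an unadjusted comparison leaves that spread in the error term and carries part of any chance baseline imbalance into the result. Baseline grip is already collected and could remove much of this.

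The plan also leaves open which grip quantity is compared: follow-up value, change or adjusted value. These differ in power, and a choice made after seeing the data would be open to challenge.

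**Working it through.** **1. The plan's own figure.** The sample size rests on a 1-point difference and an SD of 0.7 for TRS and PGIS, with alpha 0.05 and 80% power. A two-sided two-sample t-test (sidedness is not stated, so two-sided is assumed) has power 75.7% at 8 per arm and 81.2% at 9 per arm. That gives 18 in total, and 18/0.9 = 20 recruited. The figure reproduces, but it does not concern grip. The plan states no grip SD, grip effect or rho.

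**2. Assumptions for grip.** 9 per arm, normal data, equal SD at baseline and follow-up, and rho varied. Differences are in SD units.

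**3. Variance of the group difference relative to the unadjusted comparison, N = 18.**
- ANCOVA: (1 − rho²) × (N − 3)/(N − 4) = (1 − rho²) × 15/14. At rho 0.5: 0.75 × 1.071 = 0.80. At rho 0.8: 0.36 × 1.071 = 0.39.
- Change score: 2 × (1 − rho). At rho 0.5: 1.00. At rho 0.8: 0.40.
- ANCOVA break-even: 1 − rho² = 14/15, so rho = √(1/15) = 0.26.
- Worst case, rho 0: the variance ratio is 1.07. After also losing one degree of freedom (16 to 15), the confidence interval is about 4% wider.

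**4. Power at a true difference of 0.75 SD** (simulation, 40,000 trials per setting, two-sided exact Mann-Whitney rejecting at U ≤ 17). Residualised means residuals from regressing follow-up grip on baseline grip with both arms pooled.

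| rho | Mann-Whitney, follow-up value | Mann-Whitney, residualised | Mann-Whitney, change |
|---|---|---|---|
| 0 | 27% | 26% | – |
| 0.3 | 27% | 28% | 21% |
| 0.5 | 27% | 33% | 27% |
| 0.7 | 27% | 46% | 43% |
| 0.8 | 27% | 60% | 59% |
| 0.9 | 27% | 86% | 88% |

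With no true difference, each version rejects in about 4% of trials.

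**5. Difference detectable with 80% power** (noncentral t). The unadjusted t-test, with SE √(2/9) and 16 df, detects 1.41 SD. ANCOVA, with SE √(2/9 × (1 − rho²) × 15/14) and 15 df, detects 1.40/1.27/1.04/0.88/0.64 SD at rho 0.3/0.5/0.7/0.8/0.9.

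**6. Chance imbalance.** The probability that baseline means differ by more than 0.5 SD is 2 × (1 − Φ(0.5/√(2/9))) = 28.9% with 9 per arm (26.4% with 10). The average gap in those trials is 0.742 SD. There the unadjusted difference is off by rho × 0.742 on average, in the direction of the imbalance: 0.37 SD at rho 0.5 and 0.59 SD at rho 0.8. The ANCOVA estimate is within 0.005 SD of the truth on average.

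**The case against.** Three stronger readings are tempting, and the documents support none of them.

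**That the plan commits to an unadjusted Mann-Whitney test on grip.** A reader might infer this because the QUEST outcomes cite baseline and the grip outcomes do not. But TRS outcomes 1 and 6 do not cite it either, and TRS is still analysed as percent change from baseline. Silence in the outcome list therefore does not show that baseline is unused. The unadjusted comparison is the literal reading, not a stated plan. If change was meant, the gain from adjustment shrinks to almost nothing at rho 0.8 and reverses slightly at 0.9.

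**That adjustment is a free gain.** It is free only in data collection. Below rho of about 0.26 ANCOVA loses a little, and residualised Mann-Whitney power at rho 0 is about 26% against 27%. No rho can be checked here. Grip is re-measured after toxin has gone into the flexors in both arms, so rho and the equal-SD assumption are both unverified.

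**That the unadjusted result is biased.** Over randomisation it is unbiased and its type I error is intact. The errors in step 6 are conditional on an imbalance having occurred.

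Two further objections stand. Taking the p-value from a rank test and the estimate from ANCOVA invites conflict: the two disagreed on significance in about 6 to 10% of simulated trials, so one analysis must be primary. Also, the Background concern is extensor weakness, and the documents do not say that grip captures it. Baseline adjustment does not settle that.

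**Conclusion.** The point holds as a minor, inexpensive improvement. The grip analysis is unspecified, and baseline grip is collected without a stated use. Against the literal reading, adjustment gains almost nothing at rho 0.3, a modest amount at 0.5 (power 27% to 33%) and a material amount from 0.7 upward (27% to 46% or more). Against a change score, it is better at low to moderate rho and about level at 0.8 to 0.9. All sizes rest on an assumed rho, normal data, equal SDs, 9 per arm and an illustrative 0.75 SD difference. Grip supplies two of nine secondary outcomes in a pilot not sized on it. The stated sample size is unaffected.

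**What to change.** Define outcomes 4 and 9 as grip strength at weeks 6 and 12, compared between groups after adjustment for baseline grip. In the Statistical analysis paragraph, name grip and prespecify one primary analysis, either:

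- a rank-based ANCOVA, applying Mann-Whitney to residuals from the pooled regression of follow-up on baseline grip, which keeps the plan's small-sample rank test; or
- ordinary ANCOVA, reporting the adjusted difference with its 95% confidence interval.

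Label any other grip analysis, including a change score, as supportive.

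The cost is a few words in each outcome and one or two lines in the analysis text, with no new measurements or visits. The statistical price is one degree of freedom, which matters only if rho is near zero.

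### Grip is the only planned strength outcome; it can show a between-arm difference in motor weakness but cannot place it in extension, where the arms differ and where the trial's rationale lies

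*Combined protocol and SAP*

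**What the plan says.** **Rationale (section 5, Background).** One earlier randomised trial is cited for "worse extensor weakness (50% moderate weakness, 42% mild weakness) as compared to flexor". The protocol then says "it is possible that lack of subjective sense of improvement evidenced by functional rating scale was related to finger extension weakness". An open-label study in which the extensors were not always injected is contrasted: "only 15% of the patients had finger extension weakness". The first question listed as open is: "It is unclear if the perceived efficacy of BoNT in tremor reduction is diminished by associated extensor weakness".

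**Hypothesis (section 6).** It predicts that "patients in the flexors alone group will experience less motor weakness and therefore report greater global improvement in symptoms". It also allows the opposite, that "injection of the extensor compartment may be well tolerated because the injected dose is only 1/3 of the dose for the flexor compartment".

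**Arms (section 7).** Both arms receive 75U in FCR and 75U in FCU. Group 1 also receives 25U in ECR and 25U in ECU; Group 2 receives placebo there.

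**Strength outcomes (section 6).** Secondary outcome 4 is "Difference in grip strength post injection between the two groups at 6 weeks"; outcome 9 is the same at 12 weeks. The instrument is given in one line: "Grip strength will be assessed using dynamometer".

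**Other routes.** Figure 2 schedules a history and physical examination at all three visits, with no stated content. Adverse events are recorded at weeks 6 and 12 as the subject reports them (Figure 2; Safety and Data Monitoring). The Appendix holds only the tremor, patient global and clinician global forms.

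**The concern.** The hypothesis is a chain: less weakness with flexors alone, and therefore better patient-rated improvement. The Background locates that weakness in extension, and the randomised contrast lies wholly in the wrist extensors. Yet nothing in the plan requires extension to be graded, recorded as data or compared between arms. An examiner may test it, or a patient may report it, but neither route yields a graded comparison.

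The interpretation of the primary result is at stake, not its validity. If PGI-I favours either arm, or neither, the trial will have no graded extension data to help explain it, and no estimate of how often extension weakness occurred at its own extensor dose. Ungraded baseline and week 6 findings cannot be recovered later.

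**Working it through.** **1. Where the arms differ.** Group 1 total 200U; Group 2 total 150U; difference 200 − 150 = 50U = 25U ECR + 25U ECU. The flexor difference is (75 + 75) − (75 + 75) = 0.

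**2. What is measured.** Of nine secondary outcomes, two concern strength (4 and 9), and both are grip. Grip is also the only strength item in the scale descriptions, the baseline assessments and Figure 2.

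**3. What a grip difference means.** Write expected grip loss as F in Group 2 and F + E in Group 1, where F comes from the flexor toxin and E from adding the extensor toxin. Doses in the flexors are equal and allocation is randomised, so the expected between-arm difference is (F + E) − F = E. Grip therefore does inform the motor-weakness part of the hypothesis. But E is the effect on grip. The documents do not say how far grip falls when extension is weak, so E near zero is compatible with either intact or weak extension.

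**4. Wrist and finger extension are distinct.** ECR and ECU are wrist extensors. Both earlier trials injected ECR and ECU (Figure 1), but the weakness the Background stresses is largely in the fingers. Finger extensors are on neither arm's injection list. One combined score could not show which function was weak.

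**5. Sample size available.** The plan's figure reproduces. With difference 1, SD 0.7, two-sided alpha 0.05 (sidedness assumed) and 80% power, the two-sample t-test needs 8.76, so 9 per arm. Power at 9 is 81.2%, and 18/(1 − 0.10) = 20. That calculation is for TRS and PGIS, not for strength.

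**6. What 9 v 9 could show on an extension grade.** Assumptions: every patient has full strength at baseline; no, mild or moderate weakness is a change of 0, −1 or −2; there is no grading error. If a proportion p of the extensor arm is weak, the probabilities are 1 − p (none), p × 42/92 (mild) and p × 50/92 (moderate), using the 42:50 split in the Background. The flexors-alone arm has 85% none and 15% mild. Power is the summed probability of all pairs of outcomes whose exact two-sided Mann-Whitney p-value is at most 0.05.

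| Weak in extensor arm (assumed) | 20% | 30% | 40% | 50% | 60% | 75% | 92% |
|---|---|---|---|---|---|---|---|
| Power | 1% | 4% | 13% | 28% | 48% | 78% | 98% |

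If the 15% in the flexors-alone arm is split 42:50 as well, the last five figures become 11, 24, 42, 69 and 92%.

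The 92% (50% + 42%) comes from a trial with a 3:2 flexor-to-extensor ratio and possible dose doubling. The 15% comes from an open-label study with selected muscles. One rate is for extensor weakness and the other for finger extension weakness, so they may be different endpoints. They serve here only to mark out a range.

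**7. Precision.** At 9 v 9, an observed probability of superiority of 0.50 has a 95% interval of 0.26 to 0.74 (Newcombe method 5), and 0.75 has about 0.48 to 0.90.

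**8. Use of baseline grip.** With equal variances at baseline and follow-up and correlation r, the variance of a change score relative to the follow-up value alone is 2(1 − r). This is 1.0 at r = 0.5, 0.6 at r = 0.7 and 0.4 at r = 0.8. Linear adjustment for baseline gives 1 − r²: 0.75, 0.51 and 0.36. The documents give no value for r.

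**The case against.** The strongest reply is that grip already addresses the hypothesis as written, which speaks of motor weakness and not extensor weakness. Step 3 bears this out. A reader might infer that grip is uninformative because both arms lose grip from the same flexor toxin; the documents do not support that, since the shared effect cancels on average. What remains is that grip cannot localise the effect, and that a null on grip says little about extension.

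Second, extension strength is not a stated objective. The aim is efficacy, the primary outcome is PGI-I, and no mediation claim is made. This stands, and it keeps the point to an improvement rather than a defect in the main comparison.

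Third, the 3:1 ratio was chosen to limit extensor weakness. If it succeeds, rates will be low, and step 6 shows almost no power there. This also stands, and is why the extension result should be descriptive.

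Fourth, the blinded investigator both injects and rates. A recorded week 6 extension grade could hint at allocation before the week 12 ratings. Ordering the assessments protects each visit's own ratings but does not remove that carry-over.

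A reader might also infer that grip would go unanalysed, because the Mann-Whitney sentence sits under a tremor heading. Outcomes 4 and 9 already specify a between-group comparison, and that sentence can be read as general, so this is missing detail only.

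**Conclusion.** The point holds as a gap in explanatory measurement. Grip is the sole strength outcome; it can estimate the effect of the added extensor toxin on motor weakness, but it cannot attribute that effect to extension, and a null on grip would leave the extension question open. The whole 50U between-arm difference lies in the wrist extensors, and neither of the two strength outcomes grades extension.

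Two stronger inferences are not supported. The primary PGI-I comparison and its sample size are not affected. And a graded extension measure would not let this trial compare 3:1 with 3:2, because there is no 3:2 arm; it would describe weakness at 3:1 against no extensor toxin.

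The value of adding the measure depends on a weakness rate that the documents do not give for this dose. Under the stated assumptions, illustrative power stays below 30% up to a 50% rate and reaches 78% only at 75%. It is worth collecting as an estimate with an interval, not as a test.

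**What to change.** 1. Within the examination already scheduled at all three visits, grade wrist extension and finger extension of the injected arm separately (for example MRC 0–5). Do this before injection at baseline and, at weeks 6 and 12, only after TRS, QUEST, PGIS and CGIS are recorded. Add a row to Figure 2.
2. Report both grades by arm as explanatory outcomes: counts, and the probability of superiority for change from baseline with a 95% interval. Tabulate PGI-I by extension grade within arm. State that the result does not rest on a significance test and that a null is not evidence of no weakness.
3. Keep grip, and reword secondary outcomes 4 and 9 so that it is compared as change from baseline or adjusted for the baseline grip already collected. A change score improves precision only if baseline and follow-up correlate above 0.5; linear adjustment does not need that condition. Name the method.

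**Cost.** Two grades per visit on the case report form, probably about a minute of examination (assumed), and a few sentences of text. Visits, sample size and primary outcome do not change. Downsides are coarse grading, a few more descriptive outcomes, low power unless weakness is common, and the week 12 blinding risk, which a second blinded examiner would reduce if one is available. Item 3 is nearly free and worth doing even if extension is not graded.
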